Participants are eligible for participation if they 1) are over 50 and more than 6 months post-stroke, 2) live in the community, 3) have good cognition (MMSE ≥ 25 points) and 4) are able to walk at least three times weekly outside their home without hands on supervision (with or without the use of a walking aid). Participants will be excluded if they 1) have medical issues preventing them from participating in moderate to vigorous strength and balance exercises

and 2) have receptive aphasia impacting on ability to follow instructions and 3) are unable to provide informed consent.

Intervention

The programme delivered during this feasibility study will consist of a total of 12 multifactorial falls prevention group exercise sessions. Each session is 90-100 minutes in duration, followed by a 20-30 minute social activity (2 hours in total). The sessions will be offered over a period of 8 weeks, with one session in one week and two sessions in the next. Each session will comprise (a mix of) seven program components of the intervention:

1) *Falls prevention education*: Fifteen minutes of each session will be spent on an existing educational programme⁽²³⁾ that is framed on the principles of changes to health behaviour. This part of the programme is aimed to alert patients to their personal risk of falls, raise their knowledge about falls epidemiology and falls prevention. The educational information will be aimed specifically at patients after stroke.

2) *FaME group-based exercises* for strength and dynamic balance (these include some basic Tai Chi exercises). Fifteen minutes of every other training session will be spent on this part of the programme.

3) *(Preparing for) home exercises*. Selected components of both the FaME group-based exercise programme and the Otago home exercise programme will be practised in order to prepare participants to perform these at home for 10-20 minutes per day for the duration of the intervention.

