- 2) the Short Falls-Efficacy Scale-International (FES-I). The FES-I is a validated and reliable 7-item tool which measures confidence in performing a range of activities of daily living without falling.
- 3) The European Quality of Life 5 Dimensions Health Questionnaire (EQ-5D-5L)(32) measures health based on a descriptive system that defines health in terms of five dimensions: mobility, self-care, usual activities, pain/discomfort, and anxiety/depression.
- 4) the Stroke Impact Scale (SIS) assesses stroke-specific quality of life. The SIS is reliable, valid and sensitive to change.(33)

Balance and Mobility tests:

- 5) the Functional Ambulation Classification (FAC) classifies functional ambulation in patients undergoing physical therapy.(34),(35)
- 6) The Berg Balance Test (36) is a psychometrically sound measure of balance impairment for use in poststroke assessment. Given the floor and ceiling effects it is recommended that it is used in conjunction with other balance measures.
- 7) the 4-Square Step Test (37) is a reliable and valid clinical test of dynamic standing balance with high sensitivity and specificity.
- 8) the 5-Times Sit-to-Stand Test (38) is a functional mobility test that has excellent reliability as a measurement tool that correlates with knee flexors muscle strength.(39) (40)

All assessments will be conducted by an experienced physiotherapist.

During the intervention period the participants will be monitored for their adherence to the group exercise programme (attendance register kept by the therapists). The participants will also be asked to keep a record of the time they spend on their home exercise programme, and their fall events (with subsequent injuries) during the intervention period (self-reported through diary, see Appendix 3).

Quantitative data collection

During the outcome assessment participants will be individually interviewed about their experiences with the programme by an experienced physiotherapist who was not involved in delivering the FallMAP sessions. Family members involved with the patient will also be invited to consent (see Appendix 4) an interview. The Patient Information Statement for the family members can be found in Appendix 5.

Depending on the group a one-hour focus group may be undertaken. The topics guide for the interviews can be found in Appendix 6.

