As described in the risks paragraph above, expected adverse events during participation in this study include the following:

- slips, trips and falls and its consequences: cuts and abrasions, soft tissue injury, fracture.
- muscular/joint pain associated with the above or with increased physical activity.

All AEs judged by the reporting exercise instructor as having reasonable causal relationship to a study procedure or the intervention qualifies as a 'related AE'. The expression "*reasonable causal relationship*" means to convey in general that there is evidence or argument to suggest a causal relationship. An assignment of causality should be made by the exercise instructor responsible for conducting the FallMAP sessions using the definitions in the table below. All AEs judged as having a reasonable suspected causal relationship to a study procedure or the intervention (i.e. definitely, probably or possibly related) are considered to be related AEs. If required, the opinion of the participant's own GP will be sought. In the case of discrepant views on causality between the investigator and others, all parties will discuss the case. In the event that no agreement is made, Curtin University's HREC will be informed of both points of view.

| Relationship | Description |
|---------------------|--|
| Unrelated | There is no evidence of any causal relationship |
| Unlikely | There is little evidence to suggest there is a causal relationship (e.g. the event did not occur within a reasonable time after administration of the study procedure). There is another reasonable explanation for the event (e.g. the participant's clinical condition, other concomitant treatment). |
| Possible | There is some evidence to suggest a causal relationship (e.g. because the event occurs within a reasonable time after administration of the study procedure). However, the influence of other factors may have contributed to the event (e.g. the participant's clinical condition, other concomitant treatments). |
| Probable | There is evidence to suggest a causal relationship and the influence of other factors is unlikely. |
| Definitely | There is clear evidence to suggest a causal relationship and other possible contributing factors can be ruled out. |
| Not assessable | There is insufficient or incomplete evidence to make a clinical judgement of the causal relationship. |

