Any untoward occurrence (whether expected or not) that results in death, is life-threatening (refers to an event in which the subject was at risk of death at the time of the event; it does not refer to an event which hypothetically might have caused death if it were more severe), requires hospitalisation, results in persistent or significant disability or incapacity or is otherwise considered medically significant by the participant's own GP is considered a Serious Adverse Event (SAE). SAEs exclude any pre-planned hospitalisations not associated with clinical deterioration, routine treatment or monitoring of the studied indication not associated with any deterioration in condition, or elective or scheduled treatment for pre-existing conditions that did not worsen during the study.

AE/SAE Reporting

Before the start of each FallMAP session, participants will be asked whether they have experienced any AEs or SAEs. Any AEs or SAEs reported on the falls diaries will also be assessed. All reported AEs and SAEs will be recorded in the patient's case report form and assessed for causality and seriousness. For safety reasons, the CI ([name]) and the exercise instructors will discuss any recorded related AEs and SAEs reported by the exercise instructors during the sessions or as reported by the participants during their 12 weeks of participation. All related AEs and SAEs will be reported to all investigators and Curtin's Human Research Ethics Committee (HREC) by the CI within five working days of their occurrence. The research team will monitor any trends in related AEs and SAEs and bring the programme to a close, should this be deemed necessary.

To reduce the possibility of AEs and SAEs during the project the exercise deliverers (physiotherapist) will be qualified to deliver exercise programs to older people and ensure the exercises undertaken by the exercise participants are safe and clearly understood.

10. Risk Management

Any incident (including falls) of a participant during their visit to the Health and Wellness Centre (including the FallMAP exercise sessions) will be handled in accordance with the general emergency procedures of the venue (see Appendix 10). This procedure is in line with Curtin University's Incident and Hazard Reporting procedure: (https://healthandsafety.curtin.edu.au/event_and_hazard/index.cfm).

11. Data Handling & Record Keeping

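### The closed list of related adverse events omits the Not assessable grade, so a non-serious event with too little causal information gets no related-event discussion, ethics committee report or trend monitoring

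*Combined protocol and SAP*

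**What the plan says.** Section 9 (Adverse Events Reporting) asks the exercise instructor who conducts the sessions to grade the causality of each adverse event. The table offers Unrelated, Unlikely, Possible, Probable, Definitely and Not assessable. The text above it closes the related group: "i.e. definitely, probably or possibly related) are considered to be related AEs". The general definition is that a reasonable causal relationship "means to convey in general that there is evidence or argument to suggest a causal relationship". Not assessable is defined differently: "There is insufficient or incomplete evidence to make a clinical judgement of the causal relationship". No sentence says what is to be done with an event graded that way.

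The AE/SAE Reporting subsection has every reported event recorded in the case report form and assessed for causality and seriousness. It then names three further steps: discussion between the chief investigator and the instructors, reporting to all investigators and the HREC within five working days, and trend monitoring with possible closure of the programme. The last is worded "The research team will monitor any trends in related AEs and SAEs", and the other two use the same combined phrase.

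Events between sessions reach the study partly through self-report. Section 6 has participants keep a record of "fall events (with subsequent injuries) during the intervention period (self-reported through diary", and section 9 adds: "Any AEs or SAEs reported on the falls diaries will also be assessed". Participants are also asked to practise selected exercises and "perform these at home for 10-20 minutes per day for the duration of the intervention".

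**The concern.** Not assessable expresses lack of information, not absence of a link. Under the rule as written, lack of information leads to the same handling as a judgement that the intervention was not responsible. For non-serious events that weakens the review exactly where the facts are thin, for example after a fall at home that nobody saw.

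Safety is part of the acceptability objective (objective 1), and section 8 names exercise-related fatigue as something that may further raise the risk of falls. If several poorly documented events occurred between sessions, the group meant to notice a pattern would not be scheduled to look at them together. For SAEs, the second progression criterion in section 7 depends on attribution to the intervention, so the handling of an unresolved grade could also affect the decision to proceed to a full trial.

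**Working it through.** The documents state no figure on this point. The check sets the grades against the actions that follow from them.

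**Step 1: can a Not assessable event be related?** The list is introduced by i.e. and names three of six grades, so it is closed. The general definition needs evidence or argument for a link. Not assessable means that the evidence does not allow a judgement, so it does not enter by that route either.

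**Step 2: which events reach discussion, HREC reporting and trend monitoring?** The phrase in "The research team will monitor any trends in related AEs and SAEs" has two readings: related AEs plus all SAEs (reading A), or related AEs plus related SAEs (reading B).

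| Grade | Non-serious AE, A or B | SAE, reading A | SAE, reading B |
|---|---|---|---|
| Definitely, Probable, Possible | all three steps | all three steps | all three steps |
| Unlikely, Unrelated | none | all three steps | none |
| Not assessable | none | all three steps | none |

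For non-serious events the result is the same under both readings. For SAEs it depends on which reading was meant.

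**Step 3: does another provision bring the non-serious event back?**
- GP opinion: "If required, the opinion of the participant's own GP will be sought". This is discretionary and not linked to the Not assessable grade.
- Discrepant views on causality are discussed and, if unresolved, go to the HREC. That needs someone to disagree with the grade, and the planned discussion with the chief investigator covers only the related group.
- Section 7 lists the number of fall incidents among the descriptive analyses, with no causality filter. The fall is counted, but the count carries no attribution and triggers no action.

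**Step 4: progression criterion 2 (section 7).** The criterion is below 10% of SAEs attributed to the intervention. It names no qualifying grades and no denominator, so both possibilities are shown.
- Denominator of 10 participants: 0/10 = 0% passes; 1/10 = 10% is not below 10% and fails. One SAE not attributed because it was Not assessable could change the result.
- Denominator of all SAEs: with one attributed SAE among N, 1/N < 0.10 requires N > 10, so N of at least 11 (1/11 = 9.1%).

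**The case against.** The strongest reply is that little is actually hidden. Participants are asked about events before each session, diary events are assessed, all reported events go into the case report form, and falls are counted whatever their cause. This stands. A reader might infer that Not assessable events vanish from the study; the documents do not support that. What is missing is the further review, not the record.

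A second reply is that the grade may be rare. The instructor need not have seen an event to grade it. Possible requires only some evidence, such as timing, and participants have adequate cognition and attend at least weekly. This also stands. A reader might infer that home events will mostly be graded Not assessable, and support it with planned hours. Taking 8 weeks as 56 days, home exercise is 56 × 10 to 20 minutes = 9.3 to 18.7 hours. Sessions without the social activity are 12 × 90 to 100 minutes = 18 to 20 hours. The home share is then 9.3/29.3 = 32% to 18.7/36.7 = 51%. With the social activity included (12 × 2 = 24 hours), it is 9.3/33.3 = 28% to 18.7/42.7 = 44%. Neither range measures how often the grade would be used. They describe time, not information about events.

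A third reply concerns SAEs. Under reading A every SAE is discussed, reported and monitored, so loss of SAE review is possible but not established. Likewise, criterion 2 does not refer to the causality list, and section 7 also provides for a team discussion. Both limits stand.

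Finally, treating unresolved events as related is one convention, and listing them separately is another. The fix below uses both.

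**Conclusion.** The point holds firmly for non-serious events. Under either reading of the reporting text, a Not assessable event is handled like an unrelated one for discussion, HREC reporting and trend monitoring, and no other provision reliably corrects this. It arises by omission: no sentence declares such events unrelated.

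For SAEs the point is conditional. Loss of review follows only if related qualifies SAEs as well. Exclusion from criterion 2 follows only if an SAE with this grade is taken as not attributed to the intervention. The step from 0% to 10% further assumes the 10 participants as denominator, which section 7 does not state. A reader might infer that the rule decides whether the trial progresses; the documents support only that it could.

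The documents give no expected rate for the grade, so the number of affected events cannot be estimated. The point should be corrected because the rule, when followed, gives a weaker safety review where information is poorest. It does not undermine the study as a whole.

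**What to change.** 1. In section 9, after the definition of related events, add: *Events rated not assessable are handled and reported as related until further information allows another rating.*
2. In the AE/SAE Reporting subsection, state whether related applies to SAEs or only to AEs, so that discussion, HREC reporting and trend monitoring cover a defined set of events.
3. In the results, show Not assessable events on a separate line, AEs and SAEs apart, and read criterion 2 with and without the SAEs among them. That reading needs the criterion's denominator to be stated.

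The cost is a few sentences and some additional five-day reports to the HREC. The number cannot be forecast. The protocol cites falls in 45-73% of people after stroke, so some background falls will be reported as related. The separate line shows how many, and with 10 participants the extra work should be manageable. The change concerns classification and reporting only.

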4) *Interactive, virtual reality gamefied exercises*. This part of the program comprises a Kinect-based Exergame system (<http://mirarehab.com/product>) which will be used to transform existing physical therapy strength and balance exercises into fun video-games. This element is to improve enjoyment, and encourage adherence to the exercise component of the programme. In groups of two or three, participants will spend 30 minutes using this system between them. Each participant's training time and training level will be tailored to the individual, with the aim to gradually increase training impact.

5) *Getting on and off the floor / floorwork / safe landing & falls technique activities*. In groups of two or three participants, and over 12 sessions in stepwise progression of duration and difficulty, 30 minutes per session will be spent on exploring feelings of being balanced and off-balance, feelings of falling, and teaching participants how to fall safely, how to move if on the floor, and how to safely get up from the floor. A bespoke training programme (as based on similar programmes used in stroke rehabilitation) will be used. To ensure safety, all these activities/exercises will be tailored to the individual, supervised and guided on a one-to-one basis.

6) *Home falls hazard evaluation*. Participants will be issued with the Stay on Your Feet® Home Safety Checklist (booklet) and they will be asked to make their home and surrounding environment safer according to this checklist. Actions taken and barriers addressed will be discussed during (one of the) falls prevention education sessions.

7) *A social activity after the exercise session*: Participants will be invited to enjoy a (20-minute) morning/afternoon tea and socially engage with the other participants/therapists after

each session. Peer to peer support activities of sharing and phone contact will be encouraged.

The intervention will be delivered by two qualified and trained health professionals: a physiotherapist and an exercise physiologist. They will deliver the programme to 5 participants at the time, so in total two groups will be organised. Although all the activities will be delivered during a group session, exercises and activities can (and will) be tailored to (and be performed at the discretion of) the individual participants where necessary.

The detailed schedule of the FallMAP sessions is presented in Appendix 1.

Setting

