The FallMAP sessions will be delivered in room 201 of the Curtin Health and Wellness Centre, [name]. The Health and Wellness Centre has easy access in terms of public transport, (limited) patient parking and physical access.

The main research activities will be performed at the School of Physiotherapy and Exercise Science, Faculty of Health Sciences, [name] (CI).

Quantitative data collection

Participants who are willing and eligible to participate will be invited to undergo a one-hour baseline assessment in the week prior to commencement of the FallMAP programme. During this assessment eligibility will need to be confirmed. The first test during this baseline assessment will be the Standardised Mini-Mental State Examination (SMMSE; see Appendix 2). Only if the participant meets the criterion of ≥ 25 points on the SMMSE he/she will be allowed to continue with the remainder of the baseline assessment. Participants who score below 25 points will be informed that they are not eligible to enrol due to scoring below this level on the test. The researcher will advise participants to contact their GP to discuss the result. The one-hour outcome assessment will take place within one week of completing the programme.

Participant characteristics

The following participant characteristics will be collected during the baseline assessment: age (years), gender (male/female), time post-stroke (months), side of lesion (left/right), type of lesion (ischemic/hemorrhagic), self-rated health status (poor, fair, good, very good, excellent), the number of different prescribed medications, if the participant has discussed falls with their health provider (yes/no), if the participant is undertaking/has undertaken any healthy ageing or falls prevention activities (yes/no), recent falls history (fall in the past 12 months, yes/no; injured as a result of a fall, yes/no), and if the participant is able to stand up from the floor without assistance (yes/no).

Outcome measures

The following outcome measures will be administered both at the baseline and outcome assessment:

Questionnaires:

- 1) a bespoke semi-structured survey about the participants' falls prevention knowledge (11 true/false/unsure knowledge statements about falls and falls prevention).

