Semi-structured individual interviews of up to an hour's duration each will be held with the two staff members (instructors of the FallMAP sessions) within 2 weeks after all intervention

sessions have been completed. The topics guide for these interviews can be found in Appendix 7.

Study Data and Data Collection Procedures

The data collected during this study will consist of six paper questionnaires, physical (balance and lower limb strength) tests, audio-recordings (in-depth interviews), field notes (observations during the exercise classes), an attendance register and self-report diaries (home-exercise compliance and falls events). All assessments will take place in the exercise venue.

Baseline assessment

First the participants will be asked to provide written informed consent. Then the assessor (a research physiotherapist) will check the participant's level of cognition (duration: 10 minutes). If sufficient for participation (SMMSE ≥ 25 points) the participant characteristics will be collected (duration 10 minutes) followed by the six questionnaires (duration 20 minutes). Finally, the three physical tests will be administered (duration 20 minutes). All questionnaires and physical tests can be found in Appendix 2.

Outcome assessment

After the final (12th) FallMAP session each participant will be invited to undergo a one-hour outcome assessment. The research physiotherapist will repeat the five questionnaires (duration 20 minutes) and the three physical tests (20 minutes). Finally, the in-depth interview will take place (duration: 20-30 minutes).

Staff interviews will take place within two weeks of the final FallMAP session.

Screening, Recruitment and Consent Procedures

Identification and screening of participants

Participants will be identified and recruited through promotion of the project to out-patients from the researchers' local network and (if needed) promotion through the *Council on the Ageing* (COTA WA; <http://www.cotawa.org.au/>) and *Injury Matters* (<https://injurymatters.org.au/>) newsletters.

Recruitment procedures

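### The only scheduled adverse-event question is asked before each session, so no one is actively asked about harms once session 12 begins or after they stop attending

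*Combined protocol and SAP*

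**What the plan says.** **Harms.** Section 9 (AE/SAE Reporting) has one scheduled enquiry: "Before the start of each FallMAP session, participants will be asked whether they have experienced any AEs or SAEs". The same section says that events entered in the falls diaries are assessed, and that every reported event goes to the case report form and is judged for causality and seriousness. It also recognises reports from instructors during sessions and from participants over a stated 12 weeks. On causality: "An assignment of causality should be made by the exercise instructor responsible for conducting the FallMAP sessions".

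**Diary.** Section 6 (Outcome measures) gives its scope: time spent on home exercise "and their fall events (with subsequent injuries) during the intervention period (self-reported through diary, see Appendix 3".

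**End of study.** Section 6 (Quantitative data collection) sets the timing: "The one-hour outcome assessment will take place within one week of completing the programme". Under Outcome assessment: "After the final (12th) FallMAP session each participant will be invited to undergo a one-hour outcome assessment". The listed parts are five questionnaires and three physical tests, and then: "Finally, the in-depth interview will take place (duration: 20-30 minutes". No AE/SAE question is listed. On the interview, Section 6 says: "participants will be individually interviewed about their experiences with the programme by an experienced physiotherapist who was not involved in delivering the FallMAP sessions". Section 11 says the transcripts are then anonymised.

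**Stopping.** Section 8 (Withdrawal of participants) asks a person who withdraws only whether the reason may be recorded.

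**Use of the data.** Section 7 has two progression criteria: at least 70% of participants complete 9 of the 12 sessions, and fewer than 10% related SAEs. The second has no stated denominator.

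**The concern.** The question is tied to attendance. Someone who misses a session and comes back is asked on return. Two stretches of time have no question: from the start of session 12 to the outcome visit for everyone, and from the last attended session onward for anyone who stops for good.

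These stretches are not neutral. Session 12 is the last step of the floorwork and safe-landing component, which runs "over 12 sessions in stepwise progression of duration and difficulty". People who stop attending may have stopped because of a harm. Any resulting error in the count of related harms is downward.

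Two uses of the data are exposed. Non-serious related events, such as the muscle and joint pain that Section 9 expects, feed the ethics committee reports and trend monitoring. That pain is not part of the diary as Section 6 describes it, unless it accompanies a fall. Related SAEs feed criterion 2, one of only two criteria for moving to a definitive trial.

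There is also a smaller operational gap. The interviewer is independent of delivery, and causality is assigned by the instructor. The plan does not say who carries a harm from one to the other, or when.

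**Working it through.** **1. Number of questions.** Section 6 alternates one and two sessions a week over 8 weeks: 4 × 1 + 4 × 2 = 12, as stated. A full attender is asked 12 times, the last time before session 12 begins.

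**2. Unasked time, full attender.** The documents give no weekdays. I assume Monday to Friday sessions, fixed weekdays for each type of week, and the single-session week first. That gives 5 choices for the single session × 10 weekday pairs = 50 timetables.
- The Mondays of weeks 1 and 8 are 49 days apart. Session 12 falls 1 to 4 days after its Monday, and session 1 falls 0 to 4 days after its Monday.
- Session 1 to session 12: 49 + 1 − 4 = 46 days, to 49 + 4 − 0 = 53 days.
- With the outcome visit 7 days later: 53 to 60 days.
- Unasked share: 7/60 = 11.7% to 7/53 = 13.2%.

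**3. Unasked time for someone who stops after session 9.** This person still counts as compliant. Session 9 is the second session of week 6 and session 12 the second of week 8, so the gap is 14 days in all 50 timetables.
- Outcome visit on the day of session 12: 14/53 = 26.4% to 14/46 = 30.4%.
- Outcome visit 7 days later: 21/60 = 35.0% to 21/53 = 39.6%.

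**4. Number who could stop earlier.** Criterion 1 is met at 7/10 = 70%, so up to 3 of 10 may complete fewer than 9 sessions. Any of them who stopped for good has no specified question after the last session attended.

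**5. Effect of one missed related SAE on criterion 2.** Each denominator is an assumption.
- Per participant: 1/10 = 10%, which is not below 10% (fail), becomes 0/10 (pass).
- Per planned person-session: 1/(10 × 12) = 0.8%, a pass with or without the event.
- As a share of all SAEs, with one related among k: fail becomes pass for k = 2 to 10, and nothing changes at k = 11 (1/11 = 9.1%). On this reading a missed unrelated SAE works the other way: 1/11 = 9.1% (pass) becomes 1/10 = 10% (fail).

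**6. Safety window.** Section 9 refers to 12 weeks of participation. The programme lasts 8 weeks. Adding the baseline visit in the week before and the outcome visit within a week after gives at most 1 + 8 + 1 = 10 weeks. The 12 weeks match neither figure, and 12 − 8 = 4 weeks after the programme are counted or not depending on the reading.

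**7. Length of the outcome visit.** 20 + 20 + (20 to 30) = 60 to 70 minutes, against a stated hour.

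**The case against.** The strongest reply is that the plan has many other routes by which a harm can come to light:
- Instructors report events during sessions, and the incident procedure in Section 10 covers anything that happens at the Centre. Harm within session 12 itself is therefore covered.
- The diary covers falls with injuries in the intervention period, which is the most obvious path to a serious event such as a fracture. Section 9 suggests it may carry other events too.
- Section 9 accepts participants' own reports over 12 weeks, which may already run past session 12.
- Every participant is invited to the outcome visit, so stopping sessions does not by itself mean loss to follow-up. Objective 1 lists safety under acceptability, so the interview may well raise it.
- The questionnaires, diary and topic guide (Appendices 2, 3 and 6) were not seen, and any of them could hold a prompt.

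All of this stands, and it makes the gap smaller. It does not close it. Apart from the possible appendix prompts, these routes depend on someone witnessing the event or the participant volunteering it. None is specified as an AE/SAE question for a person who has stopped attending and declines the visit.

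A reader might infer that a harm mentioned at the exit interview cannot reach the case report form, or is lost once transcripts are anonymised. The documents do not support that. Section 9 sends all reported events to the form, whatever their source. The interviewer hears an identified participant in person, and anonymisation comes later. What is missing is only a named person and a time for the hand-over.

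**Conclusion.** The point holds in limited form. As written, the plan schedules no AE/SAE question from the start of session 12 or after a person stops attending. It also states no role or timing for moving a harm from the interviewer to the causality assessment. The likely result is under-ascertainment of intervention-related harm.

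On the assumed timetables the unasked time is up to 7 days (12 to 13% of follow-up) for a full attender, and 14 to 21 days (26 to 40%) for someone who stops after session 9. Whether one missed related SAE changes criterion 2 depends on the unstated denominator: it does per participant and does not per person-session.

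A reader might go further and infer that SAEs will be missed, or that the progression decision is unsound. The documents give no SAE rate, so the chance of a missed event cannot be estimated, and serious events are the ones most likely to surface through the other routes. The conclusion also assumes that the unseen appendices contain no AE/SAE prompt. A prompt at interview would shrink the gap but would not reach people who decline the visit.

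The conflict between 12 and 8 weeks is not mere wording, because that period decides which events count toward criterion 2.

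**What to change.** - Ask the Section 9 AE/SAE question at the scheduled outcome assessment, covering the time since the last attended session. Record the answer in the case report form and pass any event to the existing causality assessment.
- Have the interviewer enter any harm mentioned at interview in the same form at the time.
- Have existing staff put the same question by phone, if the person agrees, to anyone who has stopped attending or declines the outcome visit.
- Reconcile the 12 weeks in Section 9 with the 8-week programme and the outcome visit in Section 6. Apply the reconciled window to everyone for criterion 2, including those without an outcome visit.

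The cost is one question at a visit whose parts already total 60 to 70 minutes, a few calls among 10 participants, and short text changes. Section 7 places the progression discussion after the interviews, so it need not be delayed.
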